1.3 SCHEDULE OF ACTIVITIES (SOA)

	Screening/ Enrollment Visit Day -14 to +1	Day of Surgery Visit 1, Day 1	Visit 2 Day 2 POD1 AM	Visit 3 Day 2 POD1 PM	Visit 4 Day 3 POD2 AM	Visit 5 Day 3 POD2 PM	Visit 6 Day 4 POD3 AM	Visit 7 Day 5 POD3 PM	Day 30
Procedures									
Informed consent	X								
Demographics	X								
Medical history	X								
Randomization		X							
Administer study intervention ^a		X	X		X				
Concurrent medication review	X	X	X	X	X	X	X	X	
Physical exam	X	X	X	X	X	X	X	X	
Vital signs	X	X	X	X	X	X	X	X	
Height	X	X							
Weight	X	X							
Cognitive function	X								X
Delirium assessments	X	X	X	X	X	X	X	X	
RASS Score		X	X	X	X	X	X	X	
Quality of Recovery								X	
PONV		X		X		X			
Headache assessments	X	X	X	X	X	X	X	X	
Opioid consumption data	X	X	X	X	X	X	X	X	
Dietary caffeine intake	X	X	X	X	X	X	X	X	
Physical function	X								X
Safety outcomes		X	X	X	X	X	X	X	X
Hospital length of stay and disposition									X
Adverse event review and evaluation	X	X	X	X	X	X	X	X	X
Complete Case Report Forms (CRFs)	X	X	X	X	X	X	X	X	X

On the day of surgery, assessments will occur one hour after postanesthesia care unit admission. Postoperative day (POD) assessments will occur between 7:00 – 10:00 AM, and afternoon assessments will occur between 3:00 – 6:00 PM. Outcomes will be ascertained either via in-person data collection or chart review as outlined in **Section 8.1, Efficacy Assessments**. ^aA research nurse or physician assistant will oversee the drug administration and monitor blood pressure (every 5 minutes), heart rate, heart rhythm (via 5-lead electrocardiography), and continuous pulse oximetry. ^bSee **Sections 8.2 and 9.4.4** for safety outcomes and assessments. Of note, primary and secondary outcomes are primarily reported in this table. Lastly, the 30-day visit can be conducted virtually and/or by telephone as well.

The Caffeine, Postoperative Delirium, And CHange IN Outcomes after Surgery-2 (CAPACHINOS-2) Study Protocol <2.0>

Version <2.0>
<14 December 2022>

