To determine whether caffeine impacts sedation or agitation postoperatively	-- Sedation (-2 to -5), Richmond Agitation and Sedation Scale (RASS). Assessed one-hour after PACU arrival and twice daily. Timing will be aligned with CAM delirium assessment. -- Agitation (+2 to +4), RASS. Assessed one-hour after PACU arrival and twice daily. Timing will be aligned with CAM delirium assessment.	As described in the main text, caffeine enhances arousal via key neurochemical pathways. As such, caffeine may mitigate sedation and states related to hypoactive delirium in the early postoperative setting.
To determine whether caffeine reduces risk of perioperative headache	-- Headache severity (n, 10-centimeter VAS) one-hour after PACU arrival and twice daily. Timing will be aligned with CAM delirium assessment.	Preliminary clinical trial data suggest that caffeine can reduce perioperative rebound headache in habitual caffeine users. ²⁵
To determine the effects of caffeine on postoperative opioid consumption.	-- Cumulative opioid consumption, oral morphine equivalents (mg) from PACU arrival through postoperative day two afternoon.	Preliminary data suggest that intravenous caffeine, administered during

The Caffeine, Postoperative Delirium, And CHange IN Outcomes after Surgery-2 (CAPACHINOS-2) Study Protocol <2.0>

Version <2.0>
<14 December 2022>

OBJECTIVES	ENDPOINTS	JUSTIFICATION FOR ENDPOINTS
		early postoperative recovery, may lead to increased postoperative opioid consumption. ²⁰
Tertiary/Exploratory		
To determine the impact of intravenous caffeine on anesthetic emergence profiles	-- Anesthetic emergence time (minutes; time from surgical closure finish to extubation) -- Time from PACU arrival until PACU discharge criteria met (minutes)	Will help to characterize early postoperative arousal and clinical trajectory
To determine whether caffeine reduces the risk of immediate postoperative pulmonary complications	-- Composite outcome: any occurrence of the following airway/pulmonary complications from extubation through PACU stay: airway adjunct use, unplanned continuous positive airway pressure device, unplanned humidified high-flow oxygen, need for bag-mask ventilation, or reintubation.	Given the arousal effects of caffeine previously discussed, caffeine may plausibly mitigate risk of adverse airway and pulmonary complications in the immediate postoperative setting.

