6.5 CONCOMITANT THERAPY

The Caffeine, Postoperative Delirium, And CHange IN Outcomes after Surgery-2 (CAPACHINOS-2) Study Protocol <2.0>

Version <2.0>
<14 December 2022>

No other study drugs will be given. Participants will receive medications as clinically indicated by perioperative providers. Caffeine is metabolized via Cytochrome P450 1A2, and medications that inhibit, induce, or serve as substrates for this system may affect caffeine metabolism (<https://drug-interactions.medicine.iu.edu/MainTable.aspx>). Co-administration of these medications will be recorded and considered during data analysis.

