9.4 STATISTICAL ANALYSES

9.4.1 GENERAL APPROACH

For descriptive statistics, categorical outcomes will be presented as proportions (frequencies) and continuous data will be presented as means (\pm standard deviation) or medians (interquartile range). Normality of distribution will be assessed using the Shapiro-Wilk test, and parametric or non-parametric tests will be applied as appropriate. For statistical modeling, covariates will be specified in the following

The Caffeine, Postoperative Delirium, And CHange IN Outcomes after Surgery-2 (CAPACHINOS-2) Study Protocol <2.0>

Version <2.0>
<14 December 2022>

sections. All inferential testing will be two-sided, and p-values <0.05 will be considered statistically significant. 95% confidence intervals will be reported.

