9.4.2 ANALYSIS OF THE PRIMARY EFFICACY ENDPOINT(S)

As previously described, postoperative delirium will serve as the primary endpoint. The primary analytical test will be a multivariable logistic regression model that will follow the GEE approach. Independent variables will include the placebo group (reference), low-dose caffeine group, high-dose caffeine group, and *a priori* variables that may be independently predictive of delirium (e.g., age, male sex, American Society of Anesthesiologists Physical Status score, baseline cognitive function via Montreal Cognitive Assessment, baseline functional status via Instrumental Activities of Daily Living, depression, and epidural use⁸³). Baseline cohort imbalances, defined by absolute standardized differences >0.20, will also be included in this model.

Lastly, missing delirium data will be assessed for randomness using the Little's Missing Completely at Random Test. If data are missing at random, imputation will be performed, and these results will be compared to results with the actual data in the supplementary appendix. If data are not missing at random, no imputation will be performed, and the Cochran-Armitage test will be used to assess for the proportion of missing data across each arm.

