9.4.3 ANALYSIS OF THE SECONDARY ENDPOINT(S)

For secondary endpoints, a similar GEE-based approach will be used. Within- and between- group comparisons will be analyzed based on coefficients in the model. This approach also allows for flexibility with missing data. Unstandardized beta coefficients will be presented with 95% confidence intervals and p-values (<0.05 will be considered statistically significant).

For non-repeated continuous measures (e.g., delirium duration, cumulative opioid consumption) and binary outcomes (e.g., postoperative delirium, headache), we will use the same GEE modeling approach. All GEE models will use the empirical parameter estimates with an exchangeable correlation matrix. As indicated previously, models will adjust for baseline cohort imbalances. Additionally, for Quality of Recovery and headache severity, the differential effect of habitual caffeine consumption and group will be tested. This will be tested via interaction term of habitual caffeine consumption with caffeine group (placebo, low-dose caffeine group, high-dose). The daily number of caffeinated beverages will be recorded for each participant, and the resulting distribution will be analyzed and used to inform the most appropriate categorization of habitual caffeine users (e.g., non-users, low-dose, high-dose, etc.).

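### Section 9.4.3 leaves baseline opioid use and baseline headache to an imbalance trigger instead of pre-specifying them, at a modest cost in precision for two secondary endpoints

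*Protocol*

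**What the plan says.** Section 9.4.1 of the Protocol announces where covariates will be fixed: "For statistical modeling, covariates will be specified in the following" sections. Section 9.4.2 then gives, for the delirium model, a list of a priori variables chosen as possible predictors of delirium. The list ends with "depression, and epidural use". It is followed by the imbalance rule: "Baseline cohort imbalances, defined by absolute standardized differences >0.20, will also be included in this model".

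For secondary endpoints, section 9.4.3 refers to a similar GEE-based approach. For non-repeated measures, with cumulative opioid consumption as an example, it says "we will use the same GEE modeling approach". The only adjustment it spells out is "As indicated previously, models will adjust for baseline cohort imbalances". It names no covariate specific to opioid consumption. For headache severity it adds only an interaction with habitual caffeine use.

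The opioid endpoint in section 3 is "Cumulative opioid consumption, oral morphine equivalents (mg) from PACU arrival through postoperative day two afternoon". In the schedule of activities (1.3), the row "Opioid consumption data" and the headache row are both marked at screening as well as at the later visits. Section 6.5 leaves background treatment open: "Participants will receive medications as clinically indicated by perioperative providers". Section 6.3 stratifies randomization by age and sex only.

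**The concern.** Whether a covariate is worth adjusting for depends on how well it predicts the outcome, not on how far the arms happen to differ on it. A rule that admits a variable only when its standardized difference exceeds 0.20 ignores prediction. The baseline value of an outcome is usually the first candidate for adjustment. Analgesia here is not standardized and is not balanced by stratification, so preoperative opioid use could plausibly explain part of the spread in postoperative oral morphine equivalents. The same holds for the screening headache score and later headache.

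What is at stake is the width of the confidence interval for these two endpoints. Section 3 justifies the opioid endpoint by preliminary data suggesting that caffeine may increase consumption, so a sharper estimate has some value. The primary delirium analysis is not affected.

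**Working it through.** The protocol gives no standard deviation, effect size or power for opioid consumption or headache, so there is no stated figure to reproduce.

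**Inputs.** N = 250, allocation 1:1:1, about 10% dropout (9.2 and 4.1): 250/3 × 0.9 = 75 per arm. Two-sided α = 0.05 (9.4.1). Trigger 0.20 (9.4.2). The correlation ρ between the baseline covariate and the outcome is not in the document; 0.1 to 0.7 is assumed.

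**Step 1: how often the trigger fires.** For one covariate and one pair of arms, the chance difference has SE = √(2/75) = 0.163 SD. 0.20/0.163 = 1.22, so P(|difference| > 0.20) = 22%. With all 83 per arm it is 20%. For at least one of the two caffeine–placebo pairs it is 36% (75 per arm) or 33% (83 per arm).

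**Step 2: gain against no adjustment.** The residual SD falls by √(1−ρ²), equivalent to 75/(1−ρ²) patients per arm. The starting point is the difference with 80% unadjusted power, (1.960 + 0.842) × 0.163 = 0.457 SD.

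| ρ | SE ratio | Equivalent n per arm | Power |
|---|---|---|---|
| 0.1 | 0.995 | 76 | 80.4% |
| 0.3 | 0.954 | 82 | 83.6% |
| 0.5 | 0.866 | 100 | 89.9% |
| 0.7 | 0.714 | 147 | 97.5% |

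**Step 3: gain against the protocol's own rule.** This is the relevant comparison. It uses 20,000 simulated two-arm trials for each ρ, 75 per arm, with normal covariate and outcome.

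| ρ | Power: never / trigger / always | Type I error: trigger / always | SD of estimate: trigger / always |
|---|---|---|---|
| 0.3 | 79.5 / 80.5 / 82.8% | 4.6 / 5.1% | 0.1591 / 0.1568 |
| 0.5 | 79.8 / 83.3 / 89.4% | 3.5 / 4.8% | 0.1476 / 0.1408 |
| 0.7 | 79.6 / 86.4 / 97.3% | 2.6 / 4.8% | 0.1337 / 0.1169 |

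The power gaps are 82.8 − 80.5 = 2.3, 89.4 − 83.3 = 6.1 and 97.3 − 86.4 = 10.9 points. The true spread of the estimate shrinks by the factors 0.1568/0.1591 = 0.986, 0.1408/0.1476 = 0.954 and 0.1169/0.1337 = 0.874. Mean bias is about zero under all three rules. The trigger is conservative because large imbalances are removed while the unadjusted standard error is still used whenever it does not fire.

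**Limits.** The simulation applies the trigger to one pair of arms. In a three-arm model, an imbalance in another pair could also bring the covariate in, which would narrow the gap somewhat. Headache is measured repeatedly, so for that endpoint the figures are only a guide, with ρ read as the correlation between the screening score and the average later score.

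**The case against.** The first objection is that covariates for individual secondary endpoints belong in the SAP, which is not shown. This has some force, since the SAP may name them. But 9.4.1 undertakes to specify covariates in the protocol's own sections, and 9.4.3 then states a rule. The point concerns that rule, not an absent detail.

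The second is that the text does not say secondary endpoints are adjusted only for imbalances. This stands. A reader might infer that epidural use is left out of the opioid model. However, the wording about a similar or same GEE approach, and the reference back to 9.4.2, can fairly be read as carrying over the whole list, epidural use included. The text is ambiguous and supports neither reading firmly. The carried-over list still would not name preoperative opioid use or baseline headache.

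The third is that randomization protects the contrast. This also stands. A reader might infer that background analgesia can bias the arm comparison. An imbalance just under 0.20 can move a single trial's unadjusted contrast by up to 0.20ρ SD (0.10 SD, or 0.61 SE, at ρ = 0.5), but that is chance variation the confidence interval already covers.

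The fourth is that the √(1−ρ²) reductions in Step 2 overstate the benefit. They do if taken as the gain from changing this protocol, because they compare with never adjusting. Step 3 is the fair comparison.

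Finally, it is not established that the data exist in usable form. The schedule row does not define the screening opioid entry, section 8.1 speaks of perioperative consumption from medical records, and nothing says that epidural timing is recorded. Reading the screening mark as preoperative use is an inference.

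**Conclusion.** The point holds as a modest efficiency improvement for secondary endpoints. The plan neither settles whether the 9.4.2 list applies to them nor names the baseline value of opioid use or headache in any model, and its imbalance trigger will usually leave such a value out. The cost is about 2 power points at correlation 0.3, 6 at 0.5 and 11 at 0.7, and essentially nothing at 0.1. These sizes rest on assumed correlations, normal outcomes, 75 evaluable patients per arm and a pairwise trigger. There is no average bias, no inflation of type I error and no consequence for the primary conclusion.

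**What to change.** In section 9.4.3:

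- State that the 9.4.2 covariate list applies to the secondary endpoints, or give the list that does.
- For cumulative opioid consumption, pre-specify screening opioid use, together with epidural or other regional status fixed before randomization or the first study infusion, regardless of observed imbalance.
- For headache severity, pre-specify the screening headache score in the same way.
- Leave out analgesia started after the first infusion, since the study drug could influence it.

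The cost is one or two sentences. Before they are written, confirm that the screening opioid entry records preoperative use and that the timing of any epidural can be recovered. If either is not captured, the case report form needs a small clarification.

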4 STUDY DESIGN

4.1 OVERALL DESIGN

The **central hypothesis** of this study is that intravenous caffeine will reduce the incidence of postoperative delirium. This will be a Phase II, single-center, quadruple-blinded, placebo-controlled, block-randomized trial. Written informed consent will be obtained from all participants, and institutional review board approval will be obtained. The trial will follow a parallel design, and participants will be block-randomized with a 1:1:1 allocation ratio (placebo: 1.5 mg/kg caffeine: 3 mg/kg caffeine).

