6.3 MEASURES TO MINIMIZE BIAS: RANDOMIZATION AND BLINDING

As previously described, participants will be block-randomized with a 1:1:1 allocation ratio (placebo: caffeine 1.5 mg/kg: caffeine 3 mg/kg). Randomization will also be stratified by age (<75 or ≥75 years old) and sex. Older age is a risk factor for delirium, with patients 75 years of age and older having particularly high risk.¹³⁻¹⁵ Response to caffeine may also differ based on sex.⁸⁸ Stratified randomization will thus help to balance these biologically relevant, prognostic variables and mitigate selection bias. Additionally, research teams, patients, clinicians, and analysts will remain blinded to the study drug intervention. Regression models will also include adjustments for relevant confounders, and baseline imbalances, as described in **Section 9, Statistical Considerations**. Blinding can be broken, if necessary, per the physicians caring for the subject to ensure subject safety.

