8 STUDY ASSESSMENTS AND PROCEDURES

8.1 EFFICACY ASSESSMENTS

The specific timing of procedures/evaluations to be done at each study visit are outlined in **Section 1.3, Schedule of Activities (SoA)**. Details regarding major trial assessment measures are described in the following section.

Screening/Enrollment Visit

Screening visits will be performed during either preoperative clinic visits or on the morning of surgery. Trained research team members will make a determination of study eligibility based on medical chart review and concurrent discussion with potential participants. Screening forms will then be reviewed, confirmed, and signed by the study PI ([name]) anytime between the initial screening visit and surgical intervention. During this initial visit, baseline vitals will be taken and a physical exam will be performed by clinic and perioperative clinicians per clinical standards. Baseline research case report forms will be completed, as outlined in **Section 1.3, Schedule of Activities (SoA)**, by trained research team members.

Delirium Assessments

Delirium will be assessed using the long-form CAM, via in-person assessment, during hospitalization. The CAM strategy will be used to assess delirium severity,² and total delirium duration (days) will also be calculated.

Quality of Recovery

The patient-reported 15-item Quality of Recovery scale will be used.³ This scale has been chosen as a key secondary outcome assessment, as caffeine is postulated to reduce delirium and, potentially, headache, which may help with the recovery process. The scale will be administered preoperatively at baseline and on the second postoperative afternoon. Results will be ascertained and recorded via in-person assessment by the research team.

Agitation and Sedation

Given that caffeine enhances arousal, as described previously, caffeine may also prevent states of obtundation, particularly in the early postoperative setting given the possibility of residual anesthesia.

The Caffeine, Postoperative Delirium, And CHange IN Outcomes after Surgery-2 (CAPACHINOS-2) Study Protocol <2.0>

Version <2.0>
<14 December 2022>

The RASS⁴ will thus be used to assess for agitation (+2 to +4) or sedation (-2 to -5) each timepoint of delirium assessment except for preoperative baseline (where the RASS will not be administered).

Headache

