Headache presence and severity will also be assessed (10-centimeter visual analog scale, VAS) at each delirium assessment timepoint. The rationale for this outcome is that perioperative caffeine administration has been demonstrated to reduce rebound headache, particularly in habitual caffeine users.^{25,54}

Opioid Consumption

Perioperative opioid consumption will be collected via electronic medical records and converted to oral morphine equivalents as we have previously described.⁶

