9.2 SAMPLE SIZE DETERMINATION

Both caffeine groups will be compared to the placebo group based on Generalized Estimating Equation (GEE) modeling. Sample size calculations were thus conducted via GEE Tests for Multiple Proportions in a Cluster-Randomized Design with Power Analysis and Sample Size Software (2022; NCSS, LLC. Kaysville, Utah, USA).⁹⁰ Significance level (α) was set at 0.05. A baseline early postoperative delirium incidence (including the PACU timeframe) of 30% was conservatively estimated based on our preliminary trial.²⁰ A sample size of 250 participants will provide between 80-95% power assuming a baseline delirium incidence of 30%, an incidence ranging between 10-30% in the low-dose group, and an incidence between 10-15% in the high-dose group. These effect sizes are estimated from our preliminary trial data with a similar dosing range (1.7 – 4.5 mg/kg; median dose 2.5 mg/kg) and absolute risk reduction >20%.²⁰ Increased potency may be expected with older patients given the reduced pharmacologic volume of distribution⁷⁴ and a possible age-caffeine interaction effect with respect to cognition.⁷³ This sample size also accounts for an approximate 10% dropout rate. Lastly, no interim analyses are planned in relation to the primary outcome.

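### Section 9.4.3 names only a chance-imbalance rule for covariates in the secondary models, so preoperative Quality of Recovery and headache scores would usually be left out of their own outcome models, at a cost in precision

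*Protocol*

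**What the plan says.** **Covariates.** Section 9.4.1 undertakes to specify model covariates in the sections that follow it. Section 9.4.2 does so for the primary delirium model: treatment arm, a list of expected predictors of delirium (introduced as examples, and including age, male sex and the baseline Montreal Cognitive Assessment), and any variable whose absolute standardized difference exceeds 0.20. Section 9.4.3 describes the secondary models as following a similar GEE approach, and names one adjustment: "As indicated previously, models will adjust for baseline cohort imbalances".

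**Baseline scores collected.** For the 15-item Quality of Recovery scale, section 8.1 states: "The scale will be administered preoperatively at baseline and on the second postoperative afternoon". For headache it states: "Headache presence and severity will also be assessed (10-centimeter visual analog scale, VAS) at each delirium assessment timepoint". The schedule of activities (1.3) marks delirium and headache assessments at screening, so a preoperative headache score and CAM-S are also available.

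**Stratification.** Section 6.3 states: "Randomization will also be stratified by age (<75 or ≥75 years old) and sex".

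**Use of the secondary results.** Section 4.2 says that secondary outcomes, with quality of recovery and headache as its examples, could suggest benefit worth pursuing even if delirium is not reduced.

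**The concern.** A participant's preoperative score on a scale is usually among the better predictors of the postoperative score on that scale. Using it as a covariate removes explained variance from the treatment contrast. The rule in 9.4.3 does not select on predictive strength. It selects on how far the arms happen to differ, which under randomisation is a chance event. A strongly prognostic baseline score that is well balanced is left out, and a weak one that is imbalanced is put in. The model is also not settled until the data have been seen.

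What is at stake is the precision of the contrasts on which 4.2 relies if the primary result is negative, above all Quality of Recovery, which 8.1 singles out among the secondary assessments. The validity of those contrasts is not at stake.

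**Working it through.** The protocol states no power, standard deviation, target difference or baseline-to-outcome correlation for any secondary endpoint, so there is no figure of its own to reproduce here. The 80-95% power in 9.2 belongs to the delirium endpoint.

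**Inputs from the protocol**
- Total 250 (9.2) and "participants will be block-randomized with a 1:1:1 allocation ratio" (4.1), giving 250/3 = 83.3 per arm; about 75 per arm after the 10% dropout in 9.2.
- Section 9.4.1: "All inferential testing will be two-sided, and p-values <0.05 will be considered statistically significant".
- Imbalance threshold 0.20 (9.4.2).

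**Assumptions**
- Correlation r between the baseline and the postoperative score, shown from 0.1 to 0.7.
- An effect that gives 80% power without adjustment.

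**Step 1: how often the rule admits a baseline score**

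Under randomisation the standardized difference between two arms is approximately normal with mean 0 and standard error √(2/n). At n = 83.3 this is √(2/83.3) = 0.155, so P(|difference| > 0.20) = 2[1 − Φ(0.20/0.155)] = 0.197. Results across arms are simulated.

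| | 83.3 per arm | 75 per arm |
|---|---|---|
| One given pair | 0.197 | 0.221 |
| Either caffeine arm against placebo | 0.328 | 0.364 |
| Any of the three pairs | 0.400 | 0.438 |

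Even on the widest reading of the rule, a given baseline score is omitted in about 60% of trials at 83 per arm. This presumes the score is among the variables screened. Section 9.4.5 names demographics and comorbidities and does not mention baseline outcome scores.

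**Step 2: what omission costs**

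Taking the variance of the post-only contrast as 1, adjustment for baseline gives 1 − r². The noncentrality for 80% power is 1.960 + 0.842 = 2.802, a standardized difference of 2.802 × 0.155 = 0.434 at 83.3 per arm. Adjusted power is Φ(2.802/√(1 − r²) − 1.960).

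| r | Power with adjustment | Effective sample size multiplied by 1/(1 − r²) |
|---|---|---|
| 0.1 | 80.4% | 1.01 |
| 0.3 | 83.6% | 1.10 |
| 0.5 | 89.9% | 1.33 |
| 0.7 | 97.5% | 1.96 |

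Example at r = 0.5: 2.802/0.866 = 3.235; 3.235 − 1.960 = 1.275; Φ(1.275) = 0.899. The powers are the same at 75 per arm, because the effect is set to give 80% unadjusted. For headache, rated repeatedly, r is the correlation of baseline with whatever postoperative summary the model estimates.

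**Step 3: if baseline is instead a repeated response**

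Section 9.4.3 mentions comparisons both within and between groups, which could mean that baseline enters as an outcome. With free arm means at baseline, the group-by-time contrast is a change-score contrast with variance 2(1 − r). This exceeds 1 − r² by (1 − r)². At r = 0.5 it equals 1, no better than ignoring baseline; at r = 0.3 it is 1.4, against 0.91 with adjustment. If the baseline mean is constrained to be common to the arms, the model can match the efficiency of covariate adjustment.

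**Step 4: age and sex**

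If they explain an assumed 2-5% of outcome variance, 80% power becomes Φ(2.802/√0.98 − 1.960) = 81% to Φ(2.802/√0.95 − 1.960) = 82%.

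**The case against.** **This is a matter for the statistical analysis plan.** Covariates for secondary models are often left to that document, which is not available here, and 9.4.3 excludes no baseline score. That carries weight, but 9.4.1 undertakes to specify covariates in these sections and 9.4.3 then states a rule. It is the stated rule that is weak.

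**The stratification factors.** A reader might infer that age and sex are dropped from the secondary models. The protocol does not support this. Both are in the 9.4.2 model, and 9.4.3 refers back to a similar approach. The most that can be said is that carry-over is not stated, and the effect of omission would be small (Step 4).

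**The gain may not apply to every scale.** A reader might apply the same loss to CAM-S, headache and Quality of Recovery alike. Participants must be able to consent, and severe cognitive impairment that precludes consent is an exclusion (5.2), so preoperative CAM-S is likely near 0. Headache may be near its floor too. This is inference, since no baseline distribution is given, but a nearly constant covariate gains almost nothing. Quality of Recovery is the clear case.

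**The Quality of Recovery baseline is not certain.** The schedule, as it reads in the available text, has one mark for this scale, under the afternoon of postoperative day three, and none at screening. Sections 3 and 8.1 place the postoperative assessment on day two. A mark may have shifted in text extraction, but 8.1 is explicit about the preoperative administration, and the two places need to be aligned.

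**No bias results.** This is correct. Randomisation keeps the contrasts valid without the baseline score.

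**Conclusion.** The point holds as one of precision and prespecification, centred on Quality of Recovery and extending to headache severity. Section 9.4.3 lets these baseline scores into their own models through a chance event (about 20% of trials for a given pair of arms, 40% for any pair at 83 per arm), and the 9.4.2 list would not bring them in. On an assumed correlation of 0.3 to 0.5, always adjusting would raise 80% power to about 84-90%; at 0.1 the gain is 0.4 percentage points. Both the correlation and the 80% starting point are assumptions. The protocol does not support a claim of biased results, of omitted stratification factors, or of an equal loss for CAM-S. Nor is there reason to rule out every model that treats baseline as a response, since one with a common baseline mean is efficient.

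**What to change.** In 9.4.3:
- State that the Quality of Recovery model and the headache severity model each include the participant's preoperative value of that outcome as a prespecified covariate, whatever the observed imbalance. A longitudinal model with a common baseline mean across arms is an acceptable alternative.
- Do the same for 30-day physical function, which the schedule also marks at screening, after confirming that the same instrument is used at both times. The 30-day Montreal Cognitive Assessment is covered if the 9.4.2 list carries over, because its baseline is on that list.
- Confirm that age and sex from 9.4.2 carry over to all secondary models.

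In 1.3, align the Quality of Recovery row with 8.1 on the preoperative assessment, and check the day of the postoperative mark.

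The cost is a few sentences and one or two degrees of freedom per model. No new data are needed, provided the preoperative Quality of Recovery assessment in 8.1 is carried out.
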